9. PLAN OF TREATMENT

The following section describes the schedule for prescreening, treatment, and clinical and laboratory evaluations. When a chemistry panel is indicated the following tests are performed: Chem 7 (including sodium, potassium, bicarbonate, BUN, creatinine, and glucose), ALT, AST, total bilirubin, alkaline phosphatase, amylase, creatine kinase (CK), thyroid stimulating hormone (TSH), LDH and cortisol. (Note: Cortisol will only be collected when on treatment, therefore cortisol is not due at screening, EOT or 28d Follow Up visits.) Whenever a CBC is indicated, this will include differential and platelet count. This plan is summarized in the Schema.

Because one biomarker endpoint (taking place at UWCCC lead site only) is to evaluate metastatic tissue prior to and after treatment, up to 12 patients (ideally 6 per study arm) with disease amenable to biopsy will initially be requested to undergo one pretreatment biopsy and up to two post-treatment biopsies roughly three months after the start of treatment. It is our intent to have a minimum of 6 patients per study arm (up to 12 patients total) with evaluable pre-treatment and post-treatment biopsies, with post-treatment biopsies obtained from the same site as the pre-treatment biopsy and a second post-treatment biopsy from a clinically responding (or non-responding, if the initial site is a responding lesion) lesion if scans suggest a mixed response. If this is reached, subsequent patients with viable lesions amenable to biopsy will not be required to undergo these procedures. It is expected that some patients may have a baseline biopsy and not be able to undergo a repeat biopsy, and some patients may not have viable disease to biopsy, and these instances will not affect study participation.

TREATMENT:

NOTE: Correlative studies (biopsies, NaF PET/CT, blood for immune analyses, tetanus, and stool sample for microbiome analysis) will only be performed at UWCCC lead site. Other participating sites will not perform these procedures

- a. Prescreen / Eligibility (performed within 6 weeks of Day 1)
- 1. Confirm potential eligibility by history, pathology, diagnosis; no exclusions by history
- 2. CT scan of abdomen and pelvis (CT of chest as clinically indicated), bone scan
- 3. Sign consent form
- 4. Evaluation of CBC, chemistry panel, serum prostate specific antigen (PSA), serum PAP, and serum testosterone.

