pembrolizumab IV day 1 of 21-day cycles x 8 cycles

Arm 2: 100 μg pTVG-AR i.d days 1, 8 + 200 mg pembrolizumab IV day 1 of 21-day cycles,

for cycles 1, 2, 5 and 6 alternating with

100 µg pTVG-HP i.d. days 1, 8 + 200 mg pembrolizumab IV day 1 of 21-day

cycles, for cycles 3, 4, 7 and 8

Patients who have not come off trial at the end of cycle 8 (month 6) will continue to receive pembrolizumab at 3-week intervals, up to a total of 2 years (32 cycles) of treatment, or until evidence of radiographic progression. If prior to 2 years, and in the absence of radiographic progression, patients with rise in PSA (25% over month 6 value and with minimum rise of 2 ng/mL) will resume vaccination in follow-on courses:

Arm 1: 100 μg pTVG-HP i.d. days 1, 8 + 200 mg pembrolizumab IV day 1 of 21-day cycles

x 4 cycles

Arm 2: 100 μg pTVG-AR i.d days 1, 8 + 200 mg pembrolizumab IV day 1 of q 21-day

cycles, for two cycles followed by

100 µg pTVG-HP i.d. days 1, 8 + 200 mg pembrolizumab IV day 1 in 21-day

cycles, for two cycles

Eligible subjects will be randomly assigned in 1:1 fashion to either Arm 1 or Arm 2.

u. Randomization and Stratification

Eligible patients will be randomized to the two study arms with an allocation ratio of 1:1. The randomization will be stratified by institution and prior treatment (or not) with prior second generation AR targeting agents. Treatment arm assignment will be made by biostatics/investigational pharmacy after a patient has been registered.

v. Sample Size and Power Calculation

The expected 6-months PFS rate in Arm 1 (pTVG-HP DNA vaccine and Pembrolizumab) in this patient population is 20-30%. It is hypothesized that adding pTVG-AR DNA vaccine (Arm 2) will increase the 6-months PFS rate to at least 55%. The following table shows the required sample sizes for detecting various differences in the 6-months PFS rates between the two study arms, assuming 80% power and a one-sided 0.10 significance level. As this is a phase II study, a less stringent significance level of 0.10 rather than the traditional 0.05 level will be used for the primary efficacy evaluation.

Required sample sizes to detect a difference of 20-30% vs. 50-60% in the 6-months PFS rates between arms			
	6-mont	hs PFS rate in	ı Arm 2
6-months PFS rate in Arm 1	0.50	0.55	0.60
0.20	54	42	32
0.25	80	58	44
0.30	124	82	58

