The ITT population consists of all patients who are randomized. The per-protocol population consists of all evaluable patients, i.e., patients who have been treated according to protocol (all inclusion/exclusion criteria are satisfied, and adequate treatment compliance (complete treatment with pTVG-HP DNA vaccine alone or in combination with pTVG-AR DNA vaccine and Pembrolizumab to at least week 12). The safety population consists of all subjects who received at least one dose of pTVG-HP DNA vaccine with or without pTVG-AR DNA vaccine and Pembrolizumab. All primary, secondary and correlative outcomes will be analyzed for both the IIT and per-protocol population. The IIT population will be the primary analysis population. Safety will be evaluated using the safety population.

To attain 60 evaluable participants, the trial may randomize more than 60 participants if any are deemed unevaluable.

iii. Baseline Comparability

All measurements (variables) collected at baseline will be summarized and compared between study arms. These include demographic variables, ECOG PS, lab parameters (CBC, chemistry panel, serum testosterone, PSA and PAP) medical history information and CTCs. Comparisons between study arms of baseline variables on a continuous scale will be performed using a two-sample t-test and/or nonparametric Wilcoxon Rank Sum test. Comparisons between study arms of baseline variables on a categorical scale will be performed using a chi-square or Fisher's exact test.

iv. Analysis of Primary Endpoint

The 6-month PFS rate will be calculated for each study arm along with the corresponding two-sided 95% confidence interval which will be constructed using the Wilson score method. Patients who withdraw from the study without a progression or death event before the 6-month assessment will be excluded from this analysis. The stratified (by randomization strata) Mantel-Haenszel test will be used to compare the 6-months PFS rates between study arms.

v. Analysis of Secondary Endpoints

F.5.1. Overall Objective Response Rate and PSA Response Rates

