The number of responses will be summarized in tabular format, stratified by study arm. Of note, objective response rate using radiographic criteria will apply only to subjects with RECIST-measurable disease (i.e. not subjects with bone-only metastatic disease). Response rates (overall objective response and PSA response) will be calculated for each study arm along with the corresponding two-sided 95% confidence interval which will be constructed using the Wilson score method. The stratified (by randomization strata) Mantel-Haenszel test will be used to compare the overall objective response rates between study arms.

F.5.2. Progression-Free Survival and Overall Survival

Progression-Free and overall survival will be analyzed using the Kaplan-Meier method. Median PFS and OS will be calculated for each study arm and reported along with the corresponding 95% confidence intervals will which will constructed using the nonparametric Brookmeyer and Crowley method. The stratified (by randomization strata) log-rank test will be used to compare PFS and OS between study arms.

F.5.3. Antigen-specific Th1 immune Response

The number and frequencies of antigen-specific Th1 immune responses will be summarized in tabular format for each study arm and both study arms combined. A generalized linear model with a logit link function will be used to evaluate whether antigen-specific Th1 immunity elicited with treatment to either antigen (PAP or AR) is associated with PSA response. The interaction term between treatment arm and antigen-specific Th1 immune will be included in this model.

F.5.4. Analysis of Toxicity Rates and Serum Chemistry Parameters

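### Beyond the randomisation strata, no collected baseline prognostic value enters the PFS or OS comparison; baseline variables are only significance-tested between arms, which forgoes some power in these secondary analyses.

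*Combined protocol and SAP*

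**What the plan says.** **Baseline tests.** Section 11.w.iii (Baseline Comparability) opens with "All measurements (variables) collected at baseline will be summarized and compared between study arms". It continues: "These include demographic variables, ECOG PS, lab parameters (CBC, chemistry panel, serum testosterone, PSA and PAP) medical history information and CTCs". The methods are then set: "Comparisons between study arms of baseline variables on a continuous scale will be performed using a two-sample t-test and/or nonparametric Wilcoxon Rank Sum test", and "Comparisons between study arms of baseline variables on a categorical scale will be performed using a chi-square or Fisher's exact test". It does not say what follows if a test is significant, or which analysis population is used.

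**Efficacy tests.** For the primary endpoint (11.w.iv): "The stratified (by randomization strata) Mantel-Haenszel test will be used to compare the 6-months PFS rates between study arms". For PFS and OS (F.5.2): "The stratified (by randomization strata) log-rank test will be used to compare PFS and OS between study arms", with Kaplan-Meier curves and medians. No regression model is planned for either. The strata are defined in 11.u: "The randomization will be stratified by institution and prior treatment (or not) with prior second generation AR targeting agents".

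**What is collected.** Both study calendars and Section 9 place CBC, chemistry panel, PSA and PAP at screening, and ECOG performance status within four weeks of day 1. The panel includes "total bilirubin, alkaline phosphatase, amylase, creatine kinase (CK), thyroid stimulating hormone (TSH), LDH and cortisol" (cortisol is not drawn at screening). CTCs appear in neither calendar, nor in Section 9.

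**The concern.** In the full randomised set any baseline difference is due to chance, so a p-value for it answers no open question. It is also a poor screen: a sizeable imbalance can pass, and a trivial one can be flagged. With no rule for acting on a flag, the plan leaves room for adjustment chosen after the data are seen, in an open-label trial.

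The collected values could instead be put to use. Section 5 admits ECOG 0, 1 or 2 and soft-tissue and/or bone disease, and Section 6 admits patients with or without earlier chemotherapy, so outcomes may vary widely within an arm. A log-rank test that ignores strong predictors loses power, and a chance imbalance in one of them passes into the arm difference. Section 2.G says the findings will inform later confirmatory trials, so such an error would be carried forward.

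**Working it through.** **1. The plan's own power.** Section 11.v: 30 per arm, one-sided 0.10. For 25% versus 55% the pooled rate is 0.40. The null SE is √(2 × 0.40 × 0.60 / 30) = 0.1265 and the alternative SE is √((0.1875 + 0.2475) / 30) = 0.1204. Power = Φ((0.30 − 1.2816 × 0.1265) / 0.1204) = Φ(1.145) = 87.4%, as stated. All nine entries of the power table reproduce. The plan states no power for time-to-event PFS or OS.

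**2. Effect sizes.** A median of about 3 months (Section 2.G) with exponential times gives 0.5² = 25% progression-free at 6 months, inside the plan's 20–30%. Then 25% versus 55% implies a hazard ratio of ln 0.55 / ln 0.25 = 0.43. A hazard ratio of 0.6 gives 0.25^0.6 = 43.5%, below the plan's 50–60% for Arm 2. It therefore stands for a smaller effect than the one hypothesised.

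**3. Baseline tests as a screen.** With 30 per arm the SE of a baseline difference is √(2/30) = 0.258 SD. The chance of a difference above 0.25 SD is 33% per variable, and above 0.5 SD it is 5.3%. A 0.5 SD difference gives t = 0.5 / 0.258 = 1.94 and p = 0.058, so it is not flagged. Counting age, ECOG, four blood counts, 14 chemistry tests, testosterone, PSA and PAP gives 23 tests. If independent, the chance of at least one p < 0.05 is 1 − 0.95^23 = 69%.

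**4. PFS power, planned test against adjusted model.** Simulation with 30 per arm, control median 3 months and one-sided 0.10. *Assumptions:* eight non-prognostic strata (the number of sites is not given), one prognostic and two null covariates. The planned test is the stratified log-rank; the alternative is a stratified Cox model with three covariates (800 trials per setting, Monte Carlo SE up to about 1.8 points).

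| Hazard ratio | Log-HR per SD | Log-rank | Cox | Gain (points) |
|---|---|---|---|---|
| 0.43 | 0.4 | 88% | 91% | 3 |
| 0.43 | 0.6 | 85% | 90% | 5 |
| 0.43 | 0.8 | 80% | 90% | 10 |
| 0.6 | 0.4 | 57% | 62% | 5 |
| 0.6 | 0.6 | 53% | 61% | 8 |
| 0.6 | 0.8 | 51% | 61% | 10 |

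Across 2, 4 or 8 strata, with log-HR per SD of 0.4 to 0.6, the gain is about 2 to 6 points at hazard ratio 0.43 and about 4 to 10 at 0.6. With eight strata, type I error was about 10–11% for the log-rank and 11–12% for the Cox model.

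**5. Weaker predictors, and OS.** With one covariate and no strata, a hazard ratio of 1.3 per SD (log 0.26) gains 1 to 2 points: 95.8% to 96.6% at hazard ratio 0.43, and 71% to 73% at 0.6. A non-prognostic covariate gains nothing (73.1% versus 73.0%). For OS, assuming hazard ratio 0.60 and a 24-month median (about 46–48 events), hazard ratios per SD of 1.3, 1.5 and 2.0 give 65% to 67%, 65% to 68% and 53% to 66%.

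**6. Error given an imbalance.** With no true PFS effect and a prognostic imbalance of 0.4 to 0.6 SD favouring Arm 2, the unadjusted, unstratified log-rank rejects in 19%, 28% and 38% of trials (hazard ratio per SD 1.3, 1.5, 2.0). The adjusted Cox test rejects in 10%, 12% and 11%. Averaged over all randomisations, both stay near 10%.

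**7. Primary endpoint.** For 25% versus 55%, with odds ratio per SD of 1.5, 2 and 3, power goes from 89% to 88%, 90% to 91% and 89% to 92% on adjustment.

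**The case against.** - *The plan does use baseline information.* A reader might infer that no baseline factor adjusts any efficacy result. The documents do not support that: the primary, objective-response, PFS and OS tests are all stratified, and prior AR-targeted therapy is a disease-history factor. The gap is confined to the other values collected.
- *Nothing is invalid.* A reader might infer a biased or miscalibrated analysis, or an underpowered primary endpoint. Randomisation keeps the overall type I error at its nominal level, and step 7 shows almost no gain for the primary test. This objection stands in full.
- *The size is assumed.* No document gives a prognostic strength or a PFS or OS hazard ratio, and 0.6 lies outside the planned effect. This stands. It is why the results are ranges, with 0.43 shown beside 0.6.
- *Sparse strata and extra covariates cost information in 60 patients.* True, but the gain in step 4 already carries that cost.
- *Baseline tests need not test a true null.* In the per-protocol set (treated to week 12), or once early withdrawals are excluded from the primary analysis, differences may not be chance. The plan does not say which set the tests use. Descriptive summaries by set would still show this. No analysis depends on these p-values, so the 69% figure in step 3 has no decision attached.
- *A detailed SAP is promised in 11.w.i.* Adjustment is therefore unspecified and not ruled out. But nothing commits that SAP to it, and its stated deadline is only before the final data are analysed.

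**Conclusion.** The point holds for PFS and OS, as a recommended improvement. Apart from institution and prior AR-targeted therapy, no collected prognostic value enters those comparisons. The baseline tests have no stated consequence, and their list includes CTCs, which the schedules do not collect.

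The cost is modest efficiency, plus error conditional on chance imbalance. For PFS it is about 2 to 6 points of power at the effect implied by the design and about 4 to 10 points at hazard ratio 0.6. Both ranges assume exponential times and a prognostic log hazard ratio of 0.4 to 0.6 per SD. If the available predictors are weak the gain is a point or two, and if they carry no information there is none. The primary analysis is not called into question.

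**What to change.** - **11.w.iii:** give descriptive baseline summaries by arm without between-arm p-values, name the population, and remove CTCs.
- **F.5.2:** before outcomes are seen, prespecify a Cox model stratified by the randomisation strata, with two or three fixed covariates (for example log PSA, log LDH and ECOG 0 versus 1–2). Make it the PFS and OS effect estimate, alongside the stratified log-rank test. State that its hazard ratio is conditional on the covariates. In the unstratified simulations a conditional 0.43 appeared as a median unadjusted 0.45, 0.47 or 0.52 for hazard ratios per SD of 1.3, 1.5 and 2.0, so the two are not interchangeable in later planning.
- **11.w.iv:** keep the Mantel-Haenszel test. An adjusted risk difference is optional.

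The cost is SAP wording and a few lines of code, with no new data. The downsides are a proportional-hazards assumption and some loss of information if institution strata are sparse. With roughly 57–60 PFS and 46–48 OS events in the simulations, two or three covariates is the limit.

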Patients who, in the discretion of the treating physician, appear to be benefiting (e.g. declining serum PSA and/or improvement in symptoms despite new radiographic lesions), may continue in protocol treatment after discussion with the sponsor PI. Some subjects may receive NaF PET/CT scans as a standard alternative to bone scintigraphy, in which case these will be used to determine response/progression. Patients will continue to have blood drawn for immune studies, as per study calendar, up to one year after screening, even if off study prior to that time. In particular, evaluations performed at 6-month time point should be performed even if off-study prior to that time, if feasible. At the end of 6 months, patients without progression will continue to receive pembrolizumab every 3 weeks, up to 2 years (32 cycles) maximum, or until radiographic disease progression. Patients on pembrolizumab alone who have PSA rise (25% increase over month 6 value, and minimum of 2 ng/mL rise) will resume a 3-month (4-cycle) follow-on course of vaccine treatment. The goal here is to minimize treatment but maintain a prolonged time to radiographic progression. All subjects who have not come off study earlier for reasons of adverse events, physician/patient discretion or radiographic progression will come off study at the end of two years of total treatment.

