The primary endpoint of the trial will be the 6-month progression-free survival rate. Secondary clinical endpoints include objective response, PSA response, progression-free and overall survival. All subjects will undergo radiographic imaging (CT of abdomen and pelvis and bone scan) prior to treatment, and at 3-month intervals (or as clinically indicated). NaF PET/CT may be used as an alternative to bone scintigraphy if that is the institution's standard, however either bone scintigraphy or NaF PET/CT must be used for evaluation at each study time point for comparability. MRI imaging may substitute for CT, but the same type of imaging must be used to determine eligibility and progression. Radiographic disease progression and response will be defined using PCWG2 published criteria [87], and as detailed in Section 7. Based on the prior trials leading to the approval of sipuleucel-T, and because immune therapies are expected to require up to several months before radiographic responses or stabilization might be observed, the radiographic studies obtained at 3 months will not be used to define progression requiring study discontinuation. These criteria, in addition to being more standard for contemporary clinical trials in advanced prostate cancer to account for bone flair occasionally seen following active treatment by bone scans, were also specifically designed to capture late radiographic objective responses that

have been observed with immune-based therapies, including pembrolizumab and other T-cell checkpoint inhibitors [80]. Time to progression will be determined from registration for all subjects. 6-month progression-free survival will be calculated for each treatment arm, as well as the median progression-free survival.

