Progression-free survival (PFS) will be defined from randomization: Time elapsed from randomization until disease progression or death. If a patient doesn't experience a disease progression or death event before the end of the follow-up period, then the observation for this patient will be censored.

F. iRECIST Guidelines

Due to the use of immunotherapies, the trial will adopt iRECIST guidelines for assessments of radiographic responses and time to progression for this trial. This section gives a summary of iRECIST guidelines and the application to this trial. Particular attention should be paid to these criteria for the 12-week response assessment.

The following table, adapted from the iRECIST guidelines, is a snapshot of changes between

RECIST 1.1 and iRECIST guidelines.

	RECIST 1.1	iRECIST
Measurable and non-	Measurable: >10mm for visceral	Measurability as per RECIST
measurable	disease, >15mm for LN lesions,	1.1
disease, number and site		
of	Maximum 5 lesions (2 per organ)	New lesions assessed per
target disease		RECIST 1.1 but recorded
	All other disease non-target (>10mm	separately for target vs nontarget
	for LN disease)	
CR, PR, or SD	Cannot have met criteria for PD	Can have had iUPD (one or more) but not iCPD,
	before CR, PR, or SD	before iCR, iPR, or iSD
Confirmation of CR or PR	Not required for randomized trials	As per RECIST 1.1
Confirmation of SD	Not required	As per RECIST 1.1
After initial progression	Any PD precludes later CR, PR or SD	iCR/iPR/iSD can be achieved after initial iUPD.
(iUPD) but then iCR, iPR,		Sum of target lesion diameters at time of
or iSD		iCR/iPR/iSD should be noted and status should be
		reset.
		Subsequent progression after iCR/iPR/iSD should
		be another iUPD, until confirmation iCPD
New Lesions	Result in PD; recorded but not	Results in iUPD at first occurrence
	measured	
		iCPD only assigned on basis of new lesions if at
		next assessment additional new lesions appear or
		an increase in size of new lesions seen (>5mm of
		sum of new lesion target or any increase in new
		lesion non-target)
Confirmation of	Not required unless equivocal	Required
progression		
Consideration of clinical	Not included in assessment	Clinical stability is considered when deciding
status	CD• Immune Complete Response iPD• Ir	whether treatment should continue after iUPD

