pTVG-AR vaccine, both vaccine(s) and pembrolizumab treatment will be held until the toxicity resolves to Grade 1 or less. If a patient develops a second Grade 3 event (or any Grade 4 event) believed at least possibly related to pTVG-HP or pTVG-AR vaccine, no further treatments will be given. Patients will not have any dose modifications (or change in dose or schedule) of pembrolizumab in this study except as noted in section 8.1. If the toxicity does not resolve, or the criteria for resuming treatment (to Grade 1 or less as in the table below) are not met, the patient will discontinue pembrolizumab (and continuing vaccinations, if the adverse event was not believed to be immune-mediated), or discontinue both study medications (vaccine and pembrolizumab) if the adverse event was considered immune-mediated and the vaccinations were already being held. The patient will remain on study, however, with collection of radiographic and laboratory data as per protocol. The rationale for these modifications is that patients could continue to benefit in terms of anti-tumor response and this could in fact be related to the development of other autoimmune toxicities, and patients who have non-immune related toxicity from pembrolizumab could still potentially benefit from continued DNA vaccination. While rare overall, autoimmune events observed following pembrolizumab treatment of patients with melanoma typically resolved and did not necessarily lead to discontinuation of treatment.

If a subject has to hold treatment for a visit, confirm with the sponsor that the subject should skip the current visit and resume treatment at the next timepoint (i.e. if a subject has to hold drug at C7D1 due to an AE, the patient would skip C7D1, be reevaluated at C7D8 and if necessary to continuing holding, come back and resume treatment at C8D1, if allowable per protocol).

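### The primary population is named as ITT, but the primary 6-month PFS analysis drops event-free withdrawals, which biases the arm rates and can move the test if withdrawal differs by arm

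*Combined protocol and SAP*

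**What the plan says.** Section 11.w.ii defines the population: "The ITT population consists of all patients who are randomized". It then states: "The IIT population will be the primary analysis population" (IIT is evidently a misprint for ITT).

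Section 11.w.iv covers the primary endpoint. Each arm's 6-month PFS rate gets a Wilson interval, and the arms are compared by a Mantel-Haenszel test stratified by the randomization strata. It adds: "Patients who withdraw from the study without a progression or death event before the 6-month assessment will be excluded from this analysis". It gives no reason, no sensitivity analysis for withdrawals and no definition of withdrawal.

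Elsewhere the same patients are retained. Section 7.E times PFS from randomization and says of a patient with no progression or death "before the end of the follow-up period, then the observation for this patient will be censored". Section F.5.2 says: "Progression-Free and overall survival will be analyzed using the Kaplan-Meier method".

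On follow-up after treatment stops, Section 8 says of patients who discontinue for toxicity: "The patient will remain on study, however, with collection of radiographic and laboratory data as per protocol". The discontinuation criteria in Section 9 likewise keep patients monitored after they stop treatment for a list of reasons. Section 6 (Endpoints) adds that "evaluations performed at 6-month time point should be performed even if off-study prior to that time, if feasible", although the context there is immune blood sampling. Section 9.j and Section 14.aa.i, by contrast, speak of patients coming off study for toxicity, discretion or autoimmune disease.

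**The concern.** A set chosen by what happens after randomization is not the set of all randomized patients. This exclusion is also one-sided. A patient who progresses at month 2 stays in as a failure, while one who leaves event-free at month 2 disappears from numerator and denominator alike.

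Two things are at stake. The first is each arm's 6-month rate, which the primary objective sets out to determine. The second is the between-arm test: with 30 patients per arm and open-label treatment, a few more departures in one arm could move its error rate or cost power. The direction is not known in advance, because it depends on why patients leave.

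**Working it through.** **Inputs from the documents.** One-sided level 0.10, 30 patients per arm, Arm 1 rate 20-30%, Arm 2 rate at least 55% (Section 11.v). Median time to progression about 3 months (Section 2.G); under an exponential model this gives 0.5² = 25% at 6 months, which is used below. Imaging: "All subjects will undergo radiographic imaging (CT of abdomen and pelvis and bone scan) prior to treatment, and at 3-month intervals" (Section 6).

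**Assumptions.** No withdrawal rate is given. The fraction *w* excluded is set at 5%, 10% or 20% per arm, with 30 randomized per arm.

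**Plan's own figure.** For 25% vs 55% with 30 per arm, the pooled two-proportion formula is Φ{[0.30 − 1.2816·√(2·0.40·0.60/30)] / √[(0.25·0.75 + 0.55·0.45)/30]} = 0.874. This matches the 87.4% in Section 11.v.

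**Step 1: bias in one arm.** Let *p* be the true 6-month rate and *r* the true 6-month rate among those excluded. The rate among patients kept is (p − w·r)/(1 − w), which equals *p* only if r = p.

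- *Independent exponential.* Event hazard λ = −ln 0.25 per 6 months. The withdrawal hazard γ solves γ/(γ+λ)·(1 − e^−(γ+λ)) = w, and r = p(1 − e^−γ)/w. This gives r = 0.452 at w = 10% and 0.441 at 20%. Here *r* exceeds *p* because only patients still event-free can be excluded. The rate reads (0.25 − 0.0452)/0.90 = 22.8%, or (0.25 − 0.0881)/0.80 = 20.2%.
- *Independent, progression seen only at the 3- and 6-month scans.* r = 0.329 and 0.325. The rate reads 24.1% and 23.1%.
- *Every leaver would have failed.* r = 0. The rate reads 0.25/0.90 = 27.8% and 0.25/0.80 = 31.3%.

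**Step 2: the test.** The true rate is 25% in both arms. The number kept is Binomial(30, 1 − w), and successes are binomial at the Step 1 rate. The test is the unstratified Mantel-Haenszel z with hypergeometric variance, rejecting above 1.2816, by exact enumeration. With no withdrawal the error is 0.095.

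| Excluded, Arm 1 vs Arm 2 | Independent exponential | Independent, scan-only | Leavers at half the overall rate | All leavers failures | Leavers at the overall rate |
|---|---|---|---|---|---|
| 5% vs 20% | 0.056 | 0.081 | 0.141 | 0.188 | 0.101 |
| 20% vs 5% | 0.166 | 0.122 | 0.068 | 0.047 | 0.099 |
| 5% vs 10% | 0.085 | 0.095 | 0.113 | 0.125 | 0.102 |

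With equal exclusion of 10% or 20%, and the same kind of leaver in both arms, the error is 0.100-0.102 in every model.

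**Step 3: power.** For 25% vs 55% with 5% vs 20% excluded, exact power is 77% (exponential) or 81% (scan-only), against 89% with no withdrawal.

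**Step 4: the alternatives.** A Kaplan-Meier comparison at 6 months with Greenwood variance, simulated under independent withdrawal, has error of about 0.10-0.11. At 5% vs 20% with all leavers failures it reaches 0.23-0.28, worse than exclusion (0.19). Counting withdrawals as failures gives rate p − w·r. Its error is 0.095 in that same case, but 0.247 at 20% vs 5% under independent exponential withdrawal.

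**The case against.** A proportion cannot use a censored patient, so the primary analysis needs some rule for unknown 6-month status. The planned test also matches the two-proportion sample size. That explains the rule but does not make the set ITT.

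A reader might infer that the exclusion contradicts the censoring rule in Sections 7.E and F.5.2. The documents do not support that. Those sections govern time-to-event PFS, and two estimators may treat the same patient differently. The handling is inconsistent, not contradictory, and the secondary analysis gives a partial check that keeps these patients.

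A reader might also infer that unequal withdrawal by itself moves the test. It does not: in the last column of the table the error stays at 0.099-0.102.

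The numbers may be small. Sections 8 and 9 keep many patients who stop treatment under observation, and 5% vs 20% of 30 means 1.5 vs 6 patients. With imaging every 3 months, scan-only detection is the closer model for independent withdrawal, and there the error stays within 0.081-0.122 even at that imbalance. This stands as a limit on size.

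Section 11.w.ii allows extra patients to be randomized. With 34 per arm, power in Step 3 rises to 81-84%. The relief is partial: evaluability there requires treatment only to week 12, so a patient leaving event-free between week 12 and month 6 counts as evaluable and is still dropped. Extra patients restore numbers, not comparability. The detailed SAP promised in Section 11.w.i could correct the rule, but it would have to overturn explicit text.

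**Conclusion.** The point holds. The primary 6-month PFS analysis is not ITT as the plan defines it, and nothing in the plan reconciles the two statements. The arm rates are biased whenever leavers' true 6-month rate differs from the overall rate: downward if withdrawal is independent of outcome, upward if leavers would have failed. For a true 25%, the reading runs from 20.2% to 31.3% at 20% excluded.

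The test's error moves only if, in addition, withdrawal differs by arm in rate or in the kind of patient who leaves. Every magnitude rests on assumed withdrawal rates and leaver models; the all-failures case is an extreme. The direction cannot be predicted, and with few or balanced withdrawals the effect on the test is negligible. It should be fixed because the mislabelling is certain and the repair is cheap.

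It would go too far to conclude that a Kaplan-Meier test must replace the planned primary test. Step 4 shows that it can do worse than exclusion when leavers are about to fail, and it would break the link to the power table in Section 11.v.

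**What to change.** In Section 11.w.iv:

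1. Estimate each arm's 6-month PFS rate in all randomized patients by Kaplan-Meier, with its confidence interval, using the plan's own censoring rule. State how the cycle 9 scan maps to the 6-month time, so that progression found there always counts. Its nominal day is 8 × 21 + 1 = 169, ± 7 days.
2. Keep the stratified Mantel-Haenszel test, but label its set *randomized patients with known 6-month status*, not ITT.
3. Add two sensitivity comparisons in all randomized patients: the Kaplan-Meier difference at 6 months, and the Mantel-Haenszel test with event-free withdrawals counted as failures.
4. Report withdrawals and their reasons by arm. State that the primary result is not robust if these analyses disagree.
5. State that stopping treatment while remaining under observation (Sections 8 and 9) is not withdrawal. Reconcile the off-study wording in Sections 9.j and 14.aa.i with this. Section 9.j may mean only stopping treatment, since its visit is timed from the off-treatment date.

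The cost is a few sentences and a little more analysis. Kaplan-Meier assumes that withdrawal is unrelated to outcome, and its Greenwood test is slightly liberal (about 0.11). Counting withdrawals as failures brings its own bias, because it treats as failed some patients who would not have progressed. Neither should replace the planned test; each shows how far the result depends on what happened to those who left.
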